the participant pool has 76 eligible infants in our targeted age range, but infants are consistently aging into this age range and year-round recruitment efforts are conducted such that typically our laboratory have successfully completed testing of 100 to 150 infants within a year. We have a strong track-record of recruiting and testing infants from racially and linguistically diverse backgrounds. Participants are typically contacted through phone or email by trained research assistants to participate in the study. Recruiting from these established participant pool typically results in ~50% inclusion of females. The racial and ethnic composition of the sample is expected to reflect the composition of the U.S. To ensure we continue to recruit a representative percentage of minority children, we will carefully monitor enrollment and include more recruitment efforts to cater to minority children as needed.

Procedure. Parents who have indicated they are willing to be contacted for studies from the database with infants in the eligible age range will be emailed a link to the study to participate. The parents can then click on the link and follow the instructions on screen to read about the description of the study and a consent document. If the parents decide to participate, they will be instructed to read the consent form and provide online permission by recording a video of themselves reading a statement, “I have read and understand the consent document. I am this child’s parent or legal guardian and we both agree to participate in this study.” Because the infants are not able to provide assent, no assent was obtained. Parents will have the option to download and/or print the forms to retain a copy for their files. Only participants with a valid consent will be permitted to participate in the study.

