Participants will be randomly assigned to one of the three conditions: (1) Black-White, (2) Black-Black, and (3) White-White. In all conditions, infants will first view familiarization then test trials. In the familiarization trials, infants will begin by viewing four trials of familiarization. The familiarization trials will consist of two female actors facing forward and talking about infant-friendly topics like the weather, grocery shopping, school, or stars in a neutral-positive speech. The order in which actors speak and their pairings will be counterbalanced across participants. Each trial will last 10.5 seconds and be repeated four times. After familiarization, infants will view six test trials. Three of these test trials will be affiliation trials and three will be disengagement trials. In the affiliation trial, the two actors start by facing forward, turn to face each other, and then wave at each other saying “Hi!”, while smiling. In the disengagement trial, the actors start by facing forward, turn to face each other, and then make a “Hmph!” sound and turn their backs to one another. Both types of trials have the same overall length of the interaction and the actors maintained the same distance from each other throughout the trial so that they were the same distance apart during both affiliation and disengagement. Each test trial will last 3 seconds, with a still image of the actors for 15 seconds after the trial ends. Each test trial therefore will last 18 seconds. This length is in line with the maximum 20 second test trial used by the case study on Lookit (Scott et al., 2017). The affiliation and disengagement trials will be presented in an alternating order and the order will be counterbalanced across participants. Looking time at the still images will be measured at each trial. After completing the trials, parents will complete a survey that asks basic demographic information and provided an option to complete an additional, optional social network questionnaire. In this demographic survey, parents will provide racial, ethnic, and linguistic information about themselves and their infants, as well as questions about their neighborhood trust and zip code in which the infant resides. Parents will also have an option to complete a

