social network questionnaire about the people the infants see and interact with on a weekly and daily basis in the past month. Racial, ethnic, and linguistic demographic information about these individuals will be collected. Describe in detail below in *Measured variables* section.

Participants will be compensated \$5 (gift card) within approximately a week for their participation. If they complete the optional additional survey on infants' social network, they will be compensated an additional \$5. To be eligible for the gift card, the infant must be in the age range of the study (i.e., 8 months; 1 day – 15 months; 1 day) and the parent must provide and submit a valid consent statement. We will still provide compensation for the family even if they do not finish the study or we cannot use the infant's data.

Data will be excluded if we observe any parental interference during the study. We will include data as long as infants complete at least one affiliation and one disengagement trial to maximize including data as much as possible.

Measured variables.

We will use the following outcome variables: (1) Looking time during familiarization: We will record looking times during each 4 familiarization trials per infant. (2) Looking time during test trials: We will record the looking times during each 3 affiliation trials and 3 disengagement trials for each participant.

Demographic variables: (1) Infant race/ethnicity: One or more of the following categories can be used by the parent to identify their infant's race/ethnicity: American Indian or Alaska Native, Asian, Black or African American, Hispanic or Latino, White, Native Hawaiian or Other Pacific Islander, Other (which parents can specify any other race/ethnicity) (2) Infant language exposure: parents can select from the following categories: monolingual, exposure, bilingual/multilingual. Parents will also be asked to indicate what language(s) their infants are exposed to. (3) Parent education level: This will consist of 8th grade or less, 9th-12th grade no diploma, High school graduate or GED completed, Some college credit but no degree, Associate degree (AA, AS), Bachelor's degree (BA, BS, AB), Graduate or professional degree.

Exploratory variables: These measures were collected to explore questions about how infants' social environments may potentially relate to infants' looking patterns.

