Preliminary analyses. To check that attention during familiarization do not differ according to condition: A mixed ANOVA with trial number (first, second, third, and fourth) as a within-subjects factor, and condition (White-White, Black-Black, and Black-White), infants' age, and infants' sex as between-subjects factors will be run on looking time during familiarization. We predict that infants' attention will decrease as trial number increases in familiarization but no difference across conditions. To check that trial order, infants' age, and infants' sex does not influence infants' attention during test trials: A mixed ANOVA with test trial order (affiliation first or disengagement first), infants' age, and infants' sex as between-subject factor will be conducted. We do not expect any significant effects from these preliminary analyses as previously found in (Lieberman et al., 2017a). However, if any of the above factors are significant in relation to test trial looking time, we will include them as covariates in the following main ANOVA model.

Main analyses. A mixed ANOVA with condition (White-White, Black-Black, and Black-White) as a between-subjects factor and test trial number (first, second, or third) and test type (affiliation vs. disengagement) as within-subjects factors on the dependent variable of looking time during test trials will be conducted. If there is a significant interaction, each condition will be analyzed separately by performing the same repeated-measures ANOVA on test trial looking times for each condition with trial number and test trial type as within-subject factors.

References:

- Kelly, D. J., Quinn, P. C., Slater, A. M., Lee, K., Gibson, A., Smith, M., Ge, L., & Pascalis, O. (2005). Three-month-olds, but not newborns, prefer own-race faces. *Developmental Science*, 8(6), F31–F36. <https://doi.org/10.1111/j.1467-7687.2005.0434a.x>
- Kinzler, K. D., Dupoux, E., & Spelke, E. S. (2007). The native language of social cognition. *Proceedings of the National Academy of Sciences*, 104(30), 12577–12580. <https://doi.org/10.1073/pnas.0705345104>
- Liberman, Z., Woodward, A. L., & Kinzler, K. D. (2017a). Preverbal Infants Infer Third-Party Social Relationships Based on Language. *Cognitive Science*, 41(S3), 622–634. <https://doi.org/10.1111/cogs.12403>

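### The inclusion rule keeps infants with as few as two of six test trials, but the planned 3 x 2 within-subjects ANOVAs, in standard form, cannot use an infant with any trial missing

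*Combined protocol and SAP*

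**What the plan says.** **Protocol, Procedure.** On the test trials: "Three of these test trials will be affiliation trials and three will be disengagement trials". The two types alternate, with order counterbalanced across infants. On measurement: "Looking time at the still images will be measured at each trial". On inclusion: "We will include data as long as infants complete at least one affiliation and one disengagement trial", and the reason given is "to maximize including data as much as possible". The same section pays families who do not finish, so incomplete sessions are foreseen.

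**Protocol, Measured variables.** "We will record the looking times during each 3 affiliation trials and 3 disengagement trials for each participant".

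**SAP, Main analyses.** A mixed ANOVA with condition between subjects and "test trial number (first, second, or third) and test type (affiliation vs. disengagement) as within-subjects factors". After a significant interaction, "each condition will be analyzed separately by performing the same repeated-measures ANOVA on test trial looking times for each condition".

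The plan does not mention missing trials, listwise deletion, imputation, averaging over available trials or a likelihood-based model. It does not define a completed trial.

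**The concern.** The inclusion rule and the analysis model imply different analysed samples. With three trials of each type and trial number crossed with test type, each of an infant's six within-subject cells holds exactly one trial. A missed trial is therefore an empty cell. The usual repeated-measures ANOVA either deletes such an infant listwise or needs balanced data and does not run. The infants whom the rule was written to keep are then the ones lost.

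The stake is precision on condition by test type. There is also analyst discretion: if the handling is left open, the choice of software routine decides who is analysed.

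**Working it through.** **No figure to reproduce.** The plan states no sample size, power, SD or trial-loss rate. The lab's testing record ("typically our laboratory have successfully completed testing of 100 to 150 infants within a year", Sample & recruitment) is a yearly volume, not a planned N, and is not used below.

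**Step 1: which infants are affected.** Six trials give 2^6 = 64 completion patterns. The inclusion rule admits (2^3 − 1)^2 = 49 of them: 9 with two trials, 18 with three, 15 with four, 6 with five and 1 with all six. So 48 of the 49 leave an empty cell. Patterns of two or three trials all of one type (6 of 15 and 2 of 20) are not admitted. Because types alternate, an infant who stops after trial 2, 3, 4 or 5 always qualifies.

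**Step 2: what a standard routine does.** A 3 x 2 repeated-measures ANOVA on 40 simulated infants ran with all cells filled. With one cell removed from one infant, it stopped because the data were unbalanced. A linear mixed model on the same data used all 40 infants and 239 of 240 trials.

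**Step 3: share of included infants without all six trials.** Let p be the assumed loss per trial.
- Early stopping: included (1−p)^2, complete (1−p)^6, so the share lost is 1 − (1−p)^4. At p = 0.05 this is 1 − 0.8145 = 0.19.
- Independent loss: included (1−p³)^2, complete (1−p)^6, so the share lost is 1 − (1−p)^6/(1−p³)^2. At p = 0.05 this is 1 − 0.7351/0.9998 = 0.26.

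**Step 4: precision and power.** An infant with nA affiliation and nD disengagement trials carries information 1/(τ² + σ²(1/nA + 1/nD)) on the test-type difference. I assume τ = 1.5 s (SD between infants of the test-type effect) and σ = 3.5 s (trial-level SD). The share kept is the information from six-trial infants divided by that from all included infants. Approximate power is Φ(2.80·√share − 1.96), which is 80% when the share is 1. For early stopping at p = 0.05 the share is 0.879, and Φ(2.80 × 0.938 − 1.96) = Φ(0.665) = 75%.

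| Assumed loss per trial | 1% | 2% | 5% | 10% |
|---|---|---|---|---|
| Included infants lost, early stopping | 4% | 8% | 19% | 34% |
| Included infants lost, independent loss | 6% | 11% | 26% | 47% |
| Information kept, early stopping | 0.976 | 0.951 | 0.879 | 0.763 |
| Information kept, independent loss | 0.951 | 0.904 | 0.774 | 0.591 |
| Power, early stopping | 79% | 78% | 75% | 69% |
| Power, independent loss | 78% | 76% | 69% | 58% |

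Varying τ from 0 to 2.5 s moves the information kept by at most 0.02.

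**Step 5: does the alternative recover the loss?** The simulation assumed 40 infants per condition, infant SD 2 s, a trend of −0.8 s per trial number, and an effect of 1.97 s in one condition (79% power with no loss). It used the 2-df condition by test type test and 1,000 runs at 2/5/10% loss.

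| Power at 2/5/10% loss | Early stopping | Independent loss |
|---|---|---|
| Mixed model, random intercept and slope | 78/72/63% | 79/78/77% |
| Complete-case test | 77/66/50% | 75/66/51% |

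The mixed model's type I error was 3.2–5.1% (SE about 0.7 points). In 10,000 null runs per setting, an intercept-only model had type I error of 7.5–8.5%, and per-infant mean differences compared between conditions had 4.7–5.4%. A test of those differences against zero within a condition, under early stopping with a trend, held about 5%.

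**The case against.** **Losing infants is a feature of the routine, not of the text.** This is fair. The plan does not prescribe listwise deletion, though a reader might infer that it does. An ANOVA with infant as a block factor accepts unbalanced data: in one check with 3 of 40 infants missing a trial, it kept all 40 and 237 of 240 trials. But that form uses one pooled error term and ignores infant-level variation in the test-type effect, as the intercept-only model in Step 5 does. So the point is limited to the standard form. Mixed ANOVA cannot safely be read as a random-effects model either, since the SAP uses the term for between- and within-subjects factors and calls the follow-up a repeated-measures ANOVA.

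**The magnitude is all assumption, and 10% is steep.** This stands. Six trials of 18 s take 108 s, and early stopping at 10% per trial means that 1 − 0.9^6 = 47% of starters quit in that time. At 1% the power cost is one or two points.

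**The gain is uneven.** This also stands. With early stopping at 2%, the simulated gap (78% against 77%) is within simulation noise. At 10%, much of the fall to 63% is lost data that no analysis recovers.

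**A played trial with no looking naturally scores 0 s.** That is a reasonable reading of trials of fixed length with looking measured on each one. A reader might treat this as a second defect, but on its own it is only a missing detail. The definition of a completed trial still needs a line.

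**One sentence on missing cells would close the gap.** It would remove the ambiguity. A complete-case sentence would still defeat the inclusion rule, and averaging over available trials would remove the SAP's trial-number factor.

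**Conclusion.** The point holds, and the plan should be changed. The inclusion rule admits infants whom the named ANOVAs, in standard form, cannot use, and nothing in the plan resolves this. The conflict itself follows from the text and needs no assumption.

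The size does need assumptions. It runs from about one power point at 1% loss with early stopping to about 22 points (80% to 58%) at 10% independent loss. That range rests on the assumed loss rates and mechanisms, τ, σ, and a normal approximation for a single contrast.

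A reader might go on to infer that dropping incomplete infants biases the result, since early stopping may be related to attention. The documents give nothing on how loss relates to looking time or condition, so bias is possible but not shown and is not claimed. The harm is lost precision and an analysed sample that the plan leaves undefined.

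**What to change.** In the SAP, Main analyses:

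- **Primary analysis.** Fit a REML linear mixed model to trial-level looking time. Use fixed effects for condition x test type x trial number, a random infant intercept and a random test-type slope. Use Kenward-Roger or Satterthwaite degrees of freedom. Include all usable trials of every infant who meets the inclusion rule.
- **Follow-up.** Fit test type x trial number within each condition, in the same form.
- **Fallback.** If the model does not converge, use per-infant mean differences (affiliation minus disengagement), compared between conditions or tested against zero within a condition. Do not fall back on an intercept-only model in that case. If the slope variance is estimated at zero, the intercept-only model is the same fit.
- **Sensitivity and reporting.** Report the complete-six-trial ANOVA as a sensitivity analysis, and trial completion by condition.
- **Definition.** State what makes a trial completed, and whether a played trial with no looking is 0 s or missing.

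The cost is SAP wording and slightly more code, with no new data, staff or infants. The downside is reliance on a missing-at-random assumption, which should be stated.

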Design: The study will be conducted online on a platform called Lookit (lookit.mit.edu), in which participants can log on to this website to complete the study. The study will last about 10 minutes with parents providing consent via recorded videos, having their infants watch video stimuli, and then completing a demographic questionnaire after their infants finish watching the video stimuli. While infants watch the video stimuli, they are recorded via a webcam that is safely stored and accessible only by researchers. See <https://lookit.readthedocs.io/en/develop/index.html> for more details about this online platform.

The design of the study is based on Liberman et al. (2017a) but adapted for an online format. Infants will be randomly assigned to one of three conditions: (1) Black-White, (2) Black-Black, and (3) White-White. Black-White condition will consist of one White female and one Black female individual. White-White condition will consist of two White female individuals and Black-Black condition will consist of two Black female individuals. In total, there are four different White and three different Black actors. The pairings between the two actors will be counterbalanced across infants such that each actor will be presented in all conditions.

Methods:

Sample & recruitment. We will recruit infants between the age of 8 months;1 day to 15 months;1 day. No participant will be excluded on the basis of sex/gender or race and ethnicity. All participants – regardless of sex/gender, race, and ethnicity – will be randomly assigned one of the three conditions. Participants will be recruited from the Lookit participant database, in which families have voluntarily signed up to be contacted for studies in which their children are eligible for on the the platform. In addition, we will recruit from an existing University of Chicago Center for Early Childhood Research (CECR) participant pool (<http://babylab.uchicago.edu>). The participant pool has over 4000 children that range in age from birth to school age. Currently,

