Neighborhood variables: (1) Infant's current zip code: This information will be used to derive neighborhood racial demographics, neighborhood median income, and neighborhood population density at the zip code level using the most recent American Community Survey (ACS) U.S. census data. (2) Neighborhood trust: This is a parent-reported measure of whether parents judge their neighbors as trustworthy. This value will be calculated by summing responses from the "social cohesion and trust" scale from (Sampson et al., 1997).

Social network variables: (1) Network racial entropy: This value will be calculated using the R package "entropy" using parent reported social network demographics and calculated for each participant. (2) Network racial EI Index: This value will be computed using the 'egor' package and will be calculated as follows: (the number of people who are from different racial backgrounds from the child) – (the number of people who are from the same racial backgrounds

as the child)/Network Size. (3) Network size: This value will be derived from parent reported social network demographics by counting the total individuals reported in the infants' network.

Statistical Analysis Plan:

Trained research assistants will view study videos to measure how long infants looked at the familiarization trials and test trials. These research assistants will be blind to the hypotheses of the study, will not know what condition the infants were assigned to, and will not have access to identifying information, including name and birthdate, when they are coding these videos.

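### Still-image looking is scored on every completed test trial, with no requirement that the infant watched the 3 s action that defines the test type

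*Combined protocol and SAP*

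**What the plan says.** The Study Protocol (Methods, Procedure) describes the test trial in two phases: "Each test trial will last 3 seconds, with a still image of the actors for 15 seconds after the trial ends". The outcome belongs to the second phase: "Looking time at the still images will be measured at each trial". The action in the first phase separates the two types. Both start with the actors facing forward and then turning to each other. They differ only after that, with a smiling wave and greeting in one, and a dismissive sound and turned backs in the other.

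The Procedure has two rules on which data count. One is "Data will be excluded if we observe any parental interference during the study". The other is "We will include data as long as infants complete at least one affiliation and one disengagement trial", with the stated aim of keeping as much data as possible. The Measured variables section adds only "We will record the looking times during each 3 affiliation trials and 3 disengagement trials for each participant".

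The Statistical Analysis Plan gives the coders one task: "Trained research assistants will view study videos to measure how long infants looked at the familiarization trials and test trials". Its main ANOVA then takes condition as the between-subjects factor, with trial number and "test type (affiliation vs. disengagement) as within-subjects factors on the dependent variable of looking time during test trials".

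**The concern.** The study question is answered by the interaction of condition with test type. Looking at the still image is informative about test type only to the extent that the infant took in the event before it. The sessions run online ("While infants watch the video stimuli, they are recorded via a webcam"). Test trials have a set length of 3 + 15 = 18 s, and no rule holds a trial until the infant is looking, so the action can play while the infant looks elsewhere.

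Under the rules as written, that trial still counts as completed. A short or zero look at the still image is then entered as that infant's response to an affiliation or a disengagement, although it may only reflect inattention to the screen. The estimated interaction shrinks. If the result is null, the plan offers no way to tell infants who did not respond to race from infants who did not watch the event.

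**Working it through.** **Inputs.** From the documents: 3 s action, 15 s still image, three trials of each type per infant, three conditions. The documents give no sample size, power, effect size, SD or rate of missed actions, so there is no planned figure to reproduce. Everything below is an illustration under stated assumptions.

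**Step 1: follow one trial through the plan.** Suppose an infant looks away for the whole 3 s action and glances at the still image for 2 s.
- Parental interference: none, so no exclusion.
- Completion: undefined, and nothing makes it depend on attention to the action.
- Coding: 2 s of looking is recorded. No field is described for whether the action was watched.
- Main ANOVA: 2 s enters the cell for that test type.

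No section removes or flags the value.

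**Step 2: attenuation.** Let q be the share of trials with the action unwatched, unrelated to type and condition, and r the share of the test-type signal that such trials keep. The expected estimate is the true effect times 1 − q(1 − r).

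| q | r = 0 | r = 0.5 |
|---|---|---|
| 10% | 1 − 0.10 × 1 = 0.90 | 1 − 0.10 × 0.5 = 0.95 |
| 20% | 1 − 0.20 × 1 = 0.80 | 1 − 0.20 × 0.5 = 0.90 |

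Simulation agrees. Assumed inputs: 50 infants per condition, still-image looking about 8 s, residual SD 3.5 s, infant SD 2 s, values clipped to 0–15 s, 1.6 s extra looking on one type in Black-White only, and a mean of about 3 s on missed trials. Seen trials alone give 1.47–1.51 s (below 1.6 s because of clipping). With all trials kept:
- r = 0: 1.32–1.35 s at 10% missed and about 1.19 s at 20%.
- r = 0.5: about 1.40 s and 1.32 s.

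Against a midpoint of 1.49 s, 1.19/1.49 = 0.80 and 1.40/1.49 = 0.94.

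**Step 3: power, keeping unseen trials versus dropping them and averaging the rest.** These are tests on per-infant affiliation-minus-disengagement means. Ranges cover separate simulations of the same setting.

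| Assumption | 10% missed, keep v drop | 20% missed, keep v drop |
|---|---|---|
| r = 0, missed-trial mean 3 s | 64–67% v 73–74% | 47–51% v 64–65% |
| r = 0.5, missed-trial mean 3 s | 72% v 74% | 58–64% v 65–67% |
| r = 0.5, missed-trial mean 6 s | 74% v 73% | 69% v 64–65% |

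A simpler setting assumes a standardised difference of 0.5 between two conditions, 63 infants each, 80% power with all actions seen, r = 0 and no lower mean on missed trials. Keeping versus dropping gives 72–75% v 74–76% at 10% and 61–68% v 66–71% at 20%. The sample size needed to recover 80% power with the trials kept is 63/0.90² = 78 or 63/0.80² = 99 per condition.

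The estimate shrinks in every setting. The sign of the power change depends on the assumptions.

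**Step 4: what dropping does in the planned model.** If an infant with any empty cell is lost from the repeated-measures ANOVA, only those with all six trials seen remain. With independent misses that share is (1 − q)⁶, so 0.90⁶ = 0.53 and 0.80⁶ = 0.26. Power falls to about 51–54% and 26–29%, well below keeping every trial in the simpler setting. If the requirement is instead one seen trial of each type, the share kept is (1 − q³)²: (1 − 0.001)² = 0.998 and (1 − 0.008)² = 0.984.

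**The case against.** The point rests on silence. Completion could have been meant to include attention to the action. The text does not say so, and the stated aim of keeping as much data as possible suggests otherwise, but the plan does not affirmatively say that unwatched trials count. That aim is also a deliberate choice with a reason, and it deserves weight.

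A reader might infer that an infant who looked away missed the event altogether. The documents do not support that. The greeting and the dismissive sound are audible without looking, and the still image may show the final posture (its content is not described). The r = 0 column is therefore the extreme case.

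A reader might also infer that dropping unwatched trials must raise power. It need not. With half the signal retained and a 6 s mean on missed trials, keeping them does better at 20% missed. Under complete-case ANOVA, dropping can cost more than the attenuation does.

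Two further cautions stand. Attention is observed after randomisation, so excluding on it could itself select infants or trials. And the coders are described as blind to the hypotheses, condition and identifying information, but masking to test type is not stated, so it cannot be taken for granted when they judge whether the action was seen.

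These cautions narrow the claim and shape the remedy. They do not fill the gap in the rules.

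**Conclusion.** The concern holds as a gap that should be closed. As written, the plan scores trials in which the distinguishing action was not watched, and these attenuate the condition by test type estimate. With misses unrelated to type and condition, and between none and half of the signal retained, the loss is about 5–10% at 10% missed and 10–20% at 20%. The missed-action rate, the retained signal and all variance inputs are assumptions, so the true size is unknown.

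A reader might go further and say that the study is biased toward concluding that infants do not use race. The documents do not support that as a conclusion. The shrinkage cannot be sized from them, and the effect on the significance test may go either way. If missed actions differ by condition or test type, the error could run in either direction. Nothing now planned would show whether they do.

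**What to change.** Before coding starts, make these changes.

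- **Define a seen trial** in the Procedure, next to the inclusion rule: a prespecified minimum look during the part of the action where the two types differ, that is, after the actors have turned to face each other. A minimum over the full 3 s would not do, because both types open identically. The sponsor chooses the threshold.
- **Code it from the existing recordings**, with coders masked to condition and, as far as possible, to test type.
- **Apply the inclusion rule to seen trials**: at least one of each type.
- **Analyse seen trials with a trial-level mixed model**, so that infants with empty cells stay in. The present rule already admits infants with as few as one trial of each type, so the planned ANOVA needs this in any case.
- **Report unseen trials** by condition and test type, and give the all-trials analysis alongside, because exclusion on attention could itself select.
- **State the outcome window once.** The Procedure says still images, while Measured variables and the Statistical Analysis Plan speak of test trials.

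The cost is one extra coding field on video already being viewed, a short definition, a change of model and the loss of some trials. A gain in power is not guaranteed. The benefit is an estimate closer to the response to a watched event, and a count showing how often the event was not watched.
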